9.4 Capacity of Participants to Give Informed Consent

No vulnerable populations (e.g. children, cognitively impaired individuals, incarcerated individuals, or pregnant women) will be included in the study, and informed consent must be obtained directly from the participants.

10. STUDY DESIGN/METHODS

10.1 Study Overview

This is a double blind, placebo-controlled trial to assess the efficacy and safety of twice weekly intramuscular injections of ketamine in decreasing symptoms of OUD and MDD. Subjects will participate in a baseline visit to complete informed consent as well as complete assessments to evaluate study

eligibility and collect baseline data. Eligible participants will return within one week for the initial ketamine intervention procedure. Immediately prior to the interventional procedure, participants will be guided through a mindfulness-based exercise to facilitate relaxation and reduce anxiety during the intervention. Participants will be subsequently monitored for 120 minutes, during which time they will complete measures assessing their perception of the interventional experience. Participants initially assigned to the placebo group may choose to optionally complete 8 ketamine medication sessions beginning in Study WK #5.

	Groups A & B							
Visit #1: Baselir	ne Assessments		Study WK #0					
Visit #2: 1st Tx	Visit #3: 2nd Tx		Study WK #1					
Visit #4: 1st Tx	Visit #5: 2nd Tx		Study WK #2					
Visit #6: 1st Tx	Visit #7: 2nd Tx		Study WK #3					
Visit #8: 1st Tx	Visit #9: 2nd Tx		Study WK #4					
Visit #10: 1 WK follow-up	Visit #10: 1st KET Tx	Visit #11: 2nd KET Tx	Study WK #5					
Group A (Ketamine)		Placebo): Optional Visits						
Visit #11: 2 WK follow-up	Visit #12: 3rd KET Tx	Visit #13: 4th KET Tx	Study WK #6					
	Visit #14: 5th KET Tx	Visit #15: 6th KET Tx	Study WK #7					
Visit #12: 4 WK follow-up	Visit #16: 7th KET Tx	Visit #17: 8th KET Tx	Study WK #8					
	Visit #18: 1 WK follow-up		Study WK #9					
	Visit #19: 2 WK follow-up	2	Study WK #10					
		2 2	8					
			l					

Visit #20: 4 WK follow-up

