10.3 Schedule of Assessments

The instruments to be used are standardized, have good psychometric properties, and are widely used. The schedule of study assessments is provided in **Table 2**.

Table 2: Schedule of Assessments

Table 2. Schedule of Assessments			TIME POINT										
Instrument Name	Purpose	Wk 0			(Wk6)					Wk 5 (9)	Wk 6 (10)	Wk 8 (12)	
		BL	Tx1	Tx2	Tx3	Tx4	Tx5	Tx6	Tx7	Tx8	1W F/U	2W	4W
Self-Reports and Consent											170		
Informed Consent X													
Demographics Form	Sample characterization	Х											
Concurrent Medications Form	Monitor medications	Х	Х	Х	Х	Х	Х	Х	Х	Х	Х	Х	Х
Treatment Services Tracking Form	Assess treatment engagement	х	Х	Х	Х	Х	Х	х	х	Х	Х	х	х
*Time Line Follow-Back (TLFB)	Primary Outcome: opioid use (amt. and frequency)	х	х	х	х	Х	Х	х	х	х	х	х	х
Beck Depression Inventory-II	Self-reported assessment of depression symptom severity	х	х	х	Х	Х	Х	х	х	х	х	х	х
Visual Analog Scale (VAS)	Measure subjective levels of opioid craving	х	Х	х	х	Х	Х	х	х	х	Х	Х	Х
General Anxiety Disorder (GAD-7)	Self report of anxiety symptom severity	х	Х	х	х	Х	Х	х	х	х	Х	Х	Х
Mystical Experiences Questionnaire	Measure of perceptual experiences		Х	Х	Х	Х	Х	х	х	Х			
Brief Pain Inventory	Measure of pain and quality of life	х		х		Х		х		х			х
University of Rhode Island Change Assessment (URICA)	Measure of motivation for change	х		х		х		х		х			х
Insomnia Severity Index (ISI)	Assess insomnia and sleep quality	х		х		Х		х		х			х
Five Facets of Mindfulness (FFMQ)	Assess aspects of mindfulness related	х		х		Х		х		х			х
PTSD Checklist (PCL-5)	Measure of PTSD symptoms	х		х		Х		х		х			х
Fagerstrom Test of Nicotine Dependence (FTND)	Measure of nicotine dependence	Х		х		Х		Х		х			х
Assessment of the Blind	Participant Perception of Randomization									Х			
Study goals	To characterize goals for treatment	х	х	х	х	Х	х	х	х	х			
	CI	inician	Assess	ments	n	1	1	1		1	n	n	
History and Physical Exam	Eligibility assessment	Х											
Vital Signs Measurement	Obtain readings of blood pressure, pulse, temperature, respirations and pulse oximetry	х	X*	X*	X*	X*	X*	X*	Х*	X*	х	х	х
Modified Observer Alertness/Sedation Scale (MOASS)	Measure of sedation		х	х	х	х	х	х	x	х	х		
Clinical Opioid Withdrawal Scale (COWS)	Clinician assessment of opioid withdrawal symptoms	Х											
*Montgomery-Asberg Depression Rating Scale (MADRS)	Primary Outcome: Clinician assessed measure of depression symptom severity	х		х		х		х		х	х	х	х

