10.6 Intervention Visit Procedures

Prior to administration of the study compounds, participants will complete self-report questionnaires, urine testing, and clinical assessments. They will subsequently complete a 10-minute mindfulness-based psychological relaxation exercise and fill out a questionnaire regarding their study goals. Participant will be asked to disinfect their shoulder using an alcohol wipe, and the study physician will then administer the medication by intramuscular administration into the participant's deltoid muscle. Vital signs will be monitored prior to treatment, and at 45 and 90 minutes post-treatment, and blood oxygen levels will be continuously monitored using pulse oximetry. If during the post-administration observation period, ketamine administration causes an increase in systolic or diastolic blood pressure >30 mm Hg from baseline, or an increase in pulse rate >30 bpm from baseline, the measurements should be repeated after the patient has been in a resting position for 10 minutes. If the criterion is still met, then that patient will not receive further administration of ketamine and will be withdrawn from the study. After completion of the injection, participants will be monitored for 120 minutes, during which time they will undergo debriefing and complete assessments of their perceptual experience of the intervention. We will evaluate the effects of a twice weekly interventions for 4 weeks, and monitor outcomes over an additional 4-week follow-up period to inform pharmacotherapy frequency in future clinical trials. Follow-up visits may be conducted by telehealth.

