12.0 DATA MANAGEMENT

12.1 Data Analysis Plan

Baseline demographic characteristics will be collected and descriptive statistics will be used to characterize participants. Data will be collected and managed using the secure REDCap (Research Electronic Data Capture) database. Descriptive statistics for primary outcomes will include 1) the percentage of individuals completing informed consent out of the number of individuals eligible on the

initial screening and 2) the percentage of individuals that complete informed consent which complete the full protocol. Other descriptive statistics for the sample population will be analyzed, and baseline characteristics that are found to be significantly associated with other outcome measures will be included as covariates. Spaghetti plots will be produced to guide modeling outcomes as a function of time. All analyses will be conducted based on intention to treat. Subjects assigned to Group B (placebo) who complete Study Wk4 (at which time main outcomes are assessed), may choose to receive 8 ketamine treatments before completing follow-up visits. To preserve study blinding, subjects who are among the final 6 subjects being enrolled will not be unblinded until primary outcomes are assessed for all 30 subjects.

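### Placebo participants who take the optional ketamine have no MADRS scheduled in Wk 5 before their first ketamine injection, so the randomised contrast after the full eight-injection course is incomplete

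*Combined protocol and SAP*

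**What the plan says.** - **Crossover.** Section 10.1: "Participants initially assigned to the placebo group may choose to optionally complete 8 ketamine medication sessions beginning in Study WK #5". Section 12.1 adds that this applies to placebo participants "who complete Study Wk4 (at which time main outcomes are assessed), may choose to receive 8 ketamine treatments before completing follow-up visits".
- **Wk 5 visit.** The visit table in section 10.1 gives the ketamine group "Visit #10: 1 WK follow-up" and a placebo participant who opts in "Visit #10: 1st KET Tx".
- **MADRS schedule.** Table 2 (section 10.3) labels the scale "Primary Outcome: Clinician assessed measure of depression symptom severity". It is marked at baseline, Tx2, Tx4, Tx6, Tx8 and the 1-, 2- and 4-week follow-ups, and left blank at Tx1, Tx3, Tx5 and Tx7. The bracketed weeks in the column heads show that the same columns serve the optional course.
- **Self-rated depression.** The BDI-II ("Self-reported assessment of depression symptom severity") is marked at every treatment and follow-up visit, Tx1 included.
- **Order within a visit.** Section 10.6: "Prior to administration of the study compounds, participants will complete self-report questionnaires, urine testing, and clinical assessments".
- **Unblinding.** Section 12.1: "subjects who are among the final 6 subjects being enrolled will not be unblinded until primary outcomes are assessed for all 30 subjects".

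**The concern.** Section 1.3 asks about ketamine against placebo over four weeks of twice-weekly treatment. The first MADRS that reflects all eight ketamine injections is the Wk 5 follow-up. For each placebo participant who opts in, no matching untreated score is scheduled that week: the next MADRS is at Visit 11, after one ketamine injection.

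The time point matters because sections 1.3 and 12.2 place the key comparison one month after the first treatment. If visits run weekly (an assumption), day 28 after Visit 2 is the start of Wk 5, close to Visit 10. Section 12.1 instead sets main outcomes at Wk 4, and section 4.2 refers to a 4-week follow-up, a label that Table 2 attaches to Wk 8 (12).

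Two things are at stake: an intention-to-treat MADRS contrast after the full course, and a same-day MADRS baseline for the optional course. Neither can be recovered once ketamine has been given.

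**Working it through.** **1. Injections received before each MADRS** (Table 2 with the order in section 10.6)

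| MADRS at | Ketamine group | Placebo participant who opts in |
|---|---|---|
| Tx2, Tx4, Tx6, Tx8 (Wk 1 to 4) | after 1, 3, 5, 7 ketamine injections | after 1, 3, 5, 7 placebo injections |
| Visit 10 (Wk 5) | MADRS, after 8 | none scheduled |
| Visit 11 | Wk 6 MADRS, after 8 | Wk 5 MADRS, after 8 placebo and 1 ketamine |

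The four controlled scores follow 1, 3, 5 and 7 injections. None follows 8, and 1 of 8 injections (12.5%) comes after the last of them.

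**2. The plan's own figures** (section 12.3: 15 per arm, SD 15.8, seven measurements, AR(1) correlation 0.9, 80% power, alpha 0.05)

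For the mean of m measurements:
- V(m) = (1/m²) ΣΣ 0.9^|i−j|
- detectable difference = (1.960 + 0.842) × SD × √(2V/n)

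With m = 7, V = 0.7978. For n = 15: 2.802 × 15.8 × √(2 × 0.7978/15) = 14.4. For n = 12: 16.1. Both stated figures reproduce. Sidedness is not stated. A one-sided test would give 12.8 (n = 15), and a t-based calculation 15.0 and 16.9, so the two-sided normal calculation is the one that fits.

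**3. Fewer controlled measurements.** Seven is also the number of post-baseline MADRS in Table 2. Three of them (1, 2 and 4 weeks of follow-up) lose their placebo control for anyone who opts in. Power for 14.4 is Φ(14.4 / (15.8 × √(2V/15)) − 1.960).

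| Controlled measurements | V | Detectable difference, n = 15 | Detectable difference, n = 12 | Power for 14.4, n = 15 |
|---|---|---|---|---|
| 7 (as stated) | 0.7978 | 14.4 | 16.1 | 79.8% |
| 4 (all placebo participants opt in) | 0.8811 | 15.2 | 17.0 | 75.8% |
| 5 (Wk 5 added) | 0.8515 | 14.9 | 16.7 | 77.2% |

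**4. The Wk 5 visit alone, if only placebo participants without ketamine contribute.** Uptake is not given in the plan, so a range is shown. Standard error = 15.8 × √(1/15 + 1/k), where k is the number of placebo participants left.

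| k | Detectable difference | Power for 14.4 |
|---|---|---|
| 15 | 16.2 | 70% |
| 10 | 18.1 | 61% |
| 7 | 20.3 | 51% |
| 5 | 22.9 | 42% |
| 3 | 28.0 | 30% |

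**5. The final six.** At 2 per month (section 12.3), participant 25 enrols at month 12.5 and participant 30 at month 15.0. The gap is 2.5 months, about 11 weeks. With even accrual, that is the upper limit on how long participant 25 could wait after Wk 4 to be unblinded. Section 12.1 does not say which visits are attended meanwhile, or whether the optional course waits too.

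**The case against.** The case for leaving the schedule alone is substantial.

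- **The planned comparison is intact.** Section 12.1 puts main outcomes at Wk 4, when both arms have had seven injections and nobody in the placebo group has had ketamine. A reader might infer that the MADRS comparison is broken. The documents do not support that.
- **The full course is not wholly without a control.** The optional course can be declined, and the 12-to-20 visit range in section 10.2 suggests that decliners keep the ordinary follow-up with a Wk 5 MADRS. Some of the final six may also have one. So it would be wrong to say that the randomised arms are never compared after eight injections. The contrast is incomplete, and those who supply it are mostly self-selected.
- **The optional course has entry data.** The Visit 9 MADRS precedes any ketamine, and the BDI-II is taken at Visit 10. What is missing is a same-day MADRS. No hypothesis in section 12.2 analyses change within the optional course.
- **The blank at Tx1 is not peculiar to depression.** It follows an every-second-visit pattern shared with the URICA, BPI, ISI, FFMQ, PCL-5 and FTND, and the URICA carries Hypothesis 3. The blank alone does not show that the MADRS was overlooked.
- **MADRS change is secondary** under section 4.2, feasibility is primary under section 4.1, and the power effect is small.

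All of this stands and limits the point. It does not supply a Wk 5 placebo score for those who opt in, and the BDI-II is self-reported, whereas Hypothesis 1 is tested on the clinician-rated MADRS.

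**Conclusion.** The point holds as a cheap improvement. For placebo participants who opt in, no MADRS is scheduled at Visit 10 before ketamine, so the last fully randomised MADRS reflects seven of eight injections. The main effect is on what can be estimated: a full-course contrast at Wk 5 depends on who declines the option.

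The effect on power is modest: about 76% with four controlled measurements, 77% with five and 80% as stated. These figures assume that every placebo participant opts in, that the seven measurements in section 12.3 are the post-baseline MADRS of Table 2, and that they are averaged with equal spacing, as the stated figures imply. Lower uptake reduces the loss. Taken alone, the Wk 5 contrast has about 70% power for 14.4 even with 15 per arm, so it would support the Wk 4 result and not replace it.

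**What to change.** 1. In Table 2 and the visit table, schedule a MADRS for every participant at the start of Wk 5, in the same window after injection 8 in both arms. The window needs defining: the ketamine group's visit is labelled as a one-week follow-up, while Visit 10 for a placebo participant who opts in is the first of two Wk 5 injections and may fall sooner.
2. For the placebo group, take it before that participant's allocation is disclosed and before any optional ketamine.
3. Report the Wk 5 contrast alongside Wk 4, and describe Wk 4 as the effect after seven injections.
4. If an optional course starts later than Wk 5, as it might among the final six, keep the Wk 5 score for the contrast and take a separate MADRS before the first optional injection as that course's baseline. A score taken weeks later cannot serve as the Wk 5 value.
5. Reconcile the outcome time points in sections 1.3, 4.2, 12.1 and 12.2, and state in section 12.3 how many of the seven measurements are placebo-controlled.

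The cost is one more clinician scale and a slightly longer Visit 10 for the placebo group, with allocation disclosed at that visit and not before it. Participants would therefore arrive without knowing whether an injection may follow, and the eating and transport arrangements in section 13 would have to allow for that.

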5.3 Exclusion Criteria

Patients will be excluded from the study if any of the following criteria apply:

- 1. They are considered an immediate suicide risk (by Columbia Suicide Severity Rating Scale of 4 or greater, a history of a suicide attempt in the past year, or by clinician judgment) or felt to be likely to require hospitalization during the course of the study.
- 2. They have a self-reported history of illicit ketamine use, or baseline urine drug testing positive for ketamine.
- 3. They are in acute opioid withdrawal (as evidenced by a score of 5 or above on the Clinician Opioid Withdrawal Scale). These subjects will be referred for clinical detoxification and pharmacotherapy induction. Subjects may be re-assessed for study eligibility after one month of treatment with a standard of care OUD pharmacotherapy.
- 4. Subjects who meet DSM-5 criteria for current bipolar disorder.
- 5. Subjects who meet DSM-5 criteria for current or history of psychotic spectrum disorders.

- 6. Women who are pregnant or nursing, and women who do not consent to use methods of highly effective birth control during the interventional phase of the study.
- 7. Subjects with current hypertension as defined by a systolic blood pressure (SBP) >140 mmHg or a diastolic blood pressure (DBP) >90 mmHg.
- 8. Subjects with a self-reported history of delirium for any cause.
- 9. A history of allergic or other adverse reaction to ketamine.
- 10. Clinically significant abnormal laboratory values, physical exam findings or self-reported medical conditions for which a transient increase in blood pressure could be significantly detrimental (e.g. glaucoma, brain aneurysms, cardiovascular disease, or end-stage renal disease).
- 11. Electrocardiogram (ECG) findings (obtained within thirty days prior to randomization) of tachycardia, prior myocardial infarction, myocardial ischemia, or aberrant conduction).

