Columbia Suicide Severity Rating Scale	Assess for presence and severity of suicidal ideation	х											
Mini International Neuropsychiatric Interview	Assess for psychotic spectrum and bipolar disorder, presence and severity of OUD	х											
Pre-screening Questionnaire	To assess for basic eligibility criteria before completing a full baseline visit.	х											
Laboratory and Procedural Tests													
Pregnancy Test (female participants only)	Eligibility assessment		х	х	х	Х	Х	х	х	х			
Drug Screen	Eligibility assessment (benzos), secondary outcome measure		х	х	х	Х	Х	х	х	х	х	х	х
Serum blood tests (CBC, CMP)	Assessment of hemodynamic, hepatic, and renal function	X**											
Electrocardiogram (ECG)	Assessment of cardiac function	X**											

* Vital signs (blood pressure, pulse, and respiratory rate) will be obtained prior to treatment sessions, and at 45 and 90 minutes post-treatment. Pulse oximetry will be monitored immediately prior to treatment, and for 90 minutes after treatment. If there is an increase in systolic or diastolic blood pressure >30 mm Hg from baseline, or an increase in pulse rate >30 bpm from baseline, the measurements should be repeated after the patient has been in a resting position for 10 minutes. ** Will be performed for individuals with significant prior cardiac, renal or liver diseases.

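### Placebo participants can start ketamine at Wk 5 with no repeat C-SSRS or history and physical, and no stated pre-dose hold for blood pressure or suicide risk

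*Combined protocol and SAP*

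**What the plan says.** **Access to optional ketamine.** Section 10.1: "Participants initially assigned to the placebo group may choose to optionally complete 8 ketamine medication sessions beginning in Study WK #5". Section 12.1: "Subjects assigned to Group B (placebo) who complete Study Wk4 (at which time main outcomes are assessed), may choose to receive 8 ketamine treatments". No other condition is attached. Section 12.1 also says that the last six enrolled "will not be unblinded until primary outcomes are assessed for all 30 subjects".

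**Interval before the first dose in the randomized phase.** Section 10.1: "Eligible participants will return within one week for the initial ketamine intervention procedure".

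**Entry limits.** Section 5.3, criterion 1, excludes immediate suicide risk, judged "by Columbia Suicide Severity Rating Scale of 4 or greater, a history of a suicide attempt in the past year, or by clinician judgment". Criterion 7 excludes "Subjects with current hypertension as defined by a systolic blood pressure (SBP) >140 mmHg or a diastolic blood pressure (DBP) >90 mmHg".

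**Schedule.** Table 2 (section 10.3) serves both phases, with the optional-phase weeks in parentheses, and has a single baseline column at Wk 0. The row "History and Physical Exam" and the C-SSRS row, whose purpose is given as "Assess for presence and severity of suicidal ideation", carry one mark each, at baseline.

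**What continues after Wk 0.** Table 2 has vital signs, BDI-II, a drug screen and the concurrent medications form at every treatment visit, pregnancy tests at treatment visits, and MADRS (which has a suicidal-thoughts item) at Tx2, 4, 6 and 8. Section 12.6 has adverse events captured at every visit. Section 13.0 requires monitoring for psychiatric distress at every intervention visit. Section 14.0 lets the PI withdraw anyone thought to be at risk of harm, and section 15.4 withdraws those who report illicit ketamine use.

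**The concern.** The protocol sets numeric limits for two risks before anyone is enrolled. A Group B participant's first exposure to ketamine comes four to five weeks after those limits were checked, and blood pressure, suicidality and medical conditions can change in that time. As written, someone whose current C-SSRS or blood pressure would have barred entry can receive a first ketamine injection, because the only stated conditions are finishing Wk 4 and wanting to go on. The decision then rests on discretion where the protocol already has a number. What is at stake is participant safety in an optional phase, not the validity of the Wk 4 comparison.

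**Working it through.** **1. Age of the screen at first ketamine exposure.** The baseline visit is 0 to 7 days before Tx1 (10.1). Tx1 is in Wk 1 and the first optional dose is in Wk 5, so nominally 4 × 7 = 28 days later.
- Group A: 0 to 7 days.
- Group B: 28 + 0 = 28 to 28 + 7 = 35 days.
- Last six enrolled, as an illustration only: assume that dosing waits for unblinding and that accrual is 2 per month (12.3). The first of the six enrols 5 × 0.5 = 2.5 months, about 11 weeks, before the last. Its screen could then be about 11 + 5 = 16 weeks old.

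**2. Does any safeguard state a pre-dose hold?**

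| Safeguard | Section | When it acts | Stated hold before injection |
|---|---|---|---|
| Vital signs | 10.6, Table 2 | before dose, then 45 and 90 min | no cut-off for the pre-dose reading |
| Rise of more than 30 mm Hg, still present after 10 min rest | 10.6 | after injection | no; stops later doses |
| Treatment above 180/105 | 15.2 | after injection | no |
| Observation until pressure is within 20% of baseline | 13.0 | after injection | no |
| BDI-II; MADRS at Tx2, 4, 6, 8 | Table 2 | through Wk 1 to 4; BDI-II also at each optional dose | no action score |
| New suicidal ideation | 13.0 | any intervention visit | referral and DSMB alert; no hold stated |
| Adverse-event and medication review | 12.6, Table 2 | every visit | no |
| PI withdrawal | 14.0 | any time | discretionary, no threshold |

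MADRS is not marked at Tx1. On the shared schedule, the last one before the first optional dose is therefore the Tx8 assessment in Wk 4.

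**3. The 10.6 rule under its two readings.** The section does not say which *baseline* the rise is measured from.
- Pre-dose reading: from a pre-dose SBP of 160, the rule is not met up to 160 + 30 = 190. It does not cap absolute pressure.
- Wk 0 reading: entry SBP is at most 140, so a sustained post-dose SBP above 140 + 30 = 170 always meets the rule. Pressure is capped, but still only after the injection.

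**4. Illustration of why the pre-dose reading matters.** Section 15.2 gives a systolic rise of 19.6 +/- 12.8 mm Hg. Assume this is mean and SD, that rises are roughly normal, and that prior intravenous data carry over to 60 mg intramuscular. P(SBP > 180) = P(rise > 180 − start):
- from 140: z = (40 − 19.6)/12.8 = 1.59, P = 0.055
- from 150: z = (30 − 19.6)/12.8 = 0.81, P = 0.208
- from 160: z = (20 − 19.6)/12.8 = 0.03, P = 0.488

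If the rise describes only the 29.8% who had an increase, multiply by 0.298: 0.017, 0.062 and 0.145. From 160, on the pre-dose reading of *baseline*, P(20 < rise ≤ 30) = 0.488 − 0.208 ≈ 0.28 (0.08 after multiplying by 0.298). In that share of cases SBP passes 180 without meeting the 10.6 rule. The starting pressures of 150 and 160 are assumed; no document says how often they would occur.

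**The case against.** **Group B is not unwatched.** By Visit 10 these participants have had eight treatment visits with vital signs, four MADRS ratings and BDI-II at each visit. Adverse-event and medication review approximates an interval history. The section 13.0 trigger, any new suicidal ideation, is broader than a C-SSRS of 4. This stands. A reader might infer that nobody checks blood pressure or suicidality before Group B's ketamine; the documents show otherwise. What is missing is a stated result that stops the injection.

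**The contrast between arms is weaker than the screen ages suggest.** Section 10.4 allows a telehealth baseline with home or pharmacy vital signs, and both arms have a same-day pre-dose pressure. The protocol also accepts 30-day windows for inclusion criteria (5.2) and ECG (5.3), close to 28 to 35 days. This stands too. The documents do not support saying that Group B is less well screened overall. The age of the screen matters because nothing says what happens if a participant's status has changed.

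**The blood-pressure gap is not special to Group B.** Correct: the limit is re-applied at no dose in either arm, and Group A's Wk 4 doses rest on a screen about three to five weeks old. The pressure hold therefore belongs at every injection.

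**The exclusions may apply throughout.** The 5.3 list has no overall time window and speaks of current hypertension, so this reading is arguable. Against it, 10.1 places eligibility evaluation at the baseline visit, 5.2 ties inclusion to randomization, and the C-SSRS limit cannot be checked when the instrument is not scheduled again.

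**A physician injects, with the PI observing, and would not dose an unsafe participant.** Probably often true. The protocol nevertheless chose numbers at entry, and nothing carries them forward.

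**Conclusion.** The gap is real but partly mitigated. Group B's first ketamine dose is conditional only on completing Wk 4 and choosing to continue. The C-SSRS and the history and physical are then about four to five weeks old, and no text applies the 140/90 or C-SSRS limit before the injection. The finding rests on the Table 2 marks and on the absence of any hold in 10.1, 10.6, 12.1, 13.0 and 14.0; it does not depend on the blood-pressure illustration.

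Up to 15 participants are exposed. The number who would exceed a limit cannot be derived from the documents, so the percentages above are conditional on assumed starting pressures and are not expected event rates. A reader might conclude outright that a participant at 160 can reach 190 without stopping. That holds only if *baseline* in 10.6 is the pre-dose reading, which is the more natural reading but is not stated. The change is worth making on safety grounds because it is cheap and uses limits and instruments already in the protocol.

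**What to change.** - **Section 10.6, every dose, both phases:** withhold the injection if the scheduled pre-dose blood pressure, repeated after rest, exceeds 140/90.
- **Section 10.6:** define *baseline* in the rule on rises above 30 mm Hg.
- **Section 10.1 and Table 2:** before the first optional ketamine dose (Visit 10, or a delayed start), add one repeat C-SSRS and a brief interval medical history with focused exam. Withhold ketamine if C-SSRS is 4 or more or a new 5.3 exclusion has arisen.

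**Cost.** A short amendment. The pressure reading is already scheduled. The added instrument and exam fall once, on at most 15 people, and make Visit 10 slightly longer. A few optional starts may be delayed or refused. The hold may also cause a few missed doses in the randomized phase; these stay in the intention-to-treat analysis.
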